12.13. Definition of End of Study

The end of the study is defined as the date when the last patient completes Visit 10. All IRBs/RECs that have approved the study will be informed of the end of the study, site closure, and archiving procedures initiated.

13. IMPLEMENTATION CONTEXT ASSESSMENT

13.1. Participants

For the implementation assessment, clinical and managerial leaders from each health centre, intervention deliverers, and trial participants will be included.

13.2. Eligibility Criteria

For patients, the eligibility criteria are the same as those described in Section 11.3. For managerial and clinical leaders, as well as DD+ deliverers, the requirements are detailed in Table 4. It should be noted that the DD+ deliverers will be employed as part of the trial personnel; however, their insights into how the intervention is delivered are considered highly valuable for thoroughly assessing the implementation context.

Table 4. Eligibility criteria implementation assessment

| Participant | Inclusion Criteria | Exclusion Criteria |
|--------------------------------|--|--------------------|
| Managerial or clinical leaders | -Clinical or administrative manager of a HC included as a study centre - ≥ 18 years | |
| DD+ providers | -DD+ facilitators employed and trained for the trial -18 to 65 years -Technical or professional healthcare worker (e.g. physician, nurse, nurse assistant, physical therapist, respiratory therapist, social worker) | |

13.3. Sample and sampling

13.3.1. Patients

The AIM and IAM instruments will be administered to all participants in the intervention arm. For the qualitative interviews aimed at assessing feasibility and providing additional explanatory depth for implementation outcomes, a purposive sampling strategy based on a maximum variation matrix will be used. This strategy will consider participants' adherence to intervention visits, age, and sex. Participants attending at least 3 out of 6 intervention visits will be classified as having high adherence, while those attending 2 or fewer visits will be classified as having low adherence.

Table 5 displays the maximum variation matrix for sampling patients for qualitative semi structured interviews. The number in each cell indicates the number of participants with those characteristics to be sampled.

Table 5. Maximum Variation Matrix

| | Male 18-24 | Female 18-24 | Male 25-44 | Female 25-44 | Male 45-65 | Female 45-65 |
|-----------------------------|---------------|-----------------|---------------|-----------------|---------------|-----------------|
| High adherence participants | 2 | 2 | 2 | 2 | 2 | 2 |
| Low adherence participants | 2 | 2 | 2 | 2 | 2 | 2 |

* The upper limit of each age interval includes participants up to that age plus 364 days.

13.3.2. Managerial or clinical leaders

All managerial/clinical leaders from the HC will be invited to participate. Up to one leader per centre will be invited.

13.3.3. Dynamic DIALOG+ providers

Up to two DD+ previously trained providers per region (Bogotá, Cauca, Guaviare, Amazonas) will be invited to participate.

13.3. Informed Consent

For patients, the informed consent process, as stated in, will include information about the possibility of being invited to participate in qualitative interviews. Clinical and managerial leaders invited to participate will undergo an informed consent process. DD+ providers will sign a specific informed consent form related to their participation in this part of the study. Despite their contractual relationship with the trial, their participation will remain voluntary.

13.4. Implementation context assessment procedures

Procedures for patients are also described in Table 1, as an integral guide to study procedures, to avoid mistakes or confusion during data collection. The assessments relevant to the implementation context for all participants are presented in Table 6.

Table 6. Study procedures for Implementation Context Assessment

| | Sociodemographic Questionnaire | Baseline QI | 6-MA QI | FIM Baseline | AIM Baseline | IAM Baseline | FIM 6-MA | AIM 6-MA | IAM 6-MA |
|---------------|--------------------------------|-------------|---------|--------------|--------------|--------------|----------|----------|----------|
| Patients | X | | X | | | | | X | X |
| Leaders | X | X | X | X | X | X | X | X | X |
| DD+ Providers | X | X | X | X | X | X | X | X | X |

Abbreviations: QI= Qualitative Interview AIM= Acceptability of Intervention Measure; IAM= Intervention Appropriateness Measure; FIM= Feasibility Intervention Measure; 6-MA: six months assessment; DD+: Dynamic DIALOG+

At the 6-month assessment, all patients in the intervention arm will complete the acceptability and appropriateness scales as part of the outcome assessment visit. In addition, 24 patients selected through purposive sampling will participate in individual in-depth interviews to assess further implementation criteria, including fidelity, adoption, and feasibility. These interviews will also provide explanatory depth to the quantitative findings from the scales, ensuring relevant information is gathered to inform future implementation.

During the trial recruitment period, feasibility, acceptability, and appropriateness scales as well as a brief sociodemographic questionnaire will be administered to clinical and managerial leaders from each health centre, as well as to staff responsible for delivering the intervention. Instruments will be completed directly in REDCap or, if necessary, using paper-based CRFs, under the supervision of local research team members. The estimated completion time for the three scales is approximately 15 minutes. Complementary in-depth interviews will also be conducted, audio-recorded, and analysed to enhance explanatory power and explore additional implementation criteria, such as fidelity and adoption.

After the 6-month assessment, clinical and managerial leaders will again complete the feasibility, acceptability, and appropriateness scales, followed by a new round of qualitative semi-structured interviews.

Each interview is expected to last between 30 and 60 minutes.

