10. STUDY DESIGN

10.1. General Design

To assess the effectiveness and implementation context of DD+, we will conduct a Hybrid I Randomised Controlled Trial (RCT) using a mixed-methods approach (11,12,40). A health economic analysis will also be included to evaluate the cost of delivering the intervention in the local setting. Effectiveness will be assessed through an RCT, implementation will be evaluated through a descriptive mixed-methods implementation study, and cost-effectiveness will be assessed through an embedded health economic analysis.

Patients in selected HC (Health Centres) will be pre-screened for chronic physical and mental health conditions. Those who meet the initial criteria will be recruited. After accepting to participate and signing informed consent, they will undergo full screening for physical and mental health conditions and QoL. Patients with co-existing physical and mental NCD will be randomised to the active intervention or the control group. Healthcare practitioners (contracted research study professional/staff) trained in DD+ will deliver the assigned intervention to each active intervention participant once per month for six months. Participants allocated to the control group will continue their usual or routine care as established by the HC professionals and procedures. Participants in the control group will be contacted periodically by phone (**Figure 1**).

[figure not shown]
Participants in both study arms will be assessed for outcome measures at baseline, 6, and 12 months. **Table 2** displays the timing and content of study procedures, including interventions, assessments, and interviews across all study visits.

To assess the **implementation context**, a mixed-methods approach will be used, with the following steps:

- a) At the 6-month assessment, all patients in the intervention arm will complete the AIM and IAM scales.
- b) At the 6-month assessment, a subsample of the intervention group participants will be invited to individual interviews to enhance explanatory power and to assess additional implementation criteria, including fidelity, adoption, and feasibility.

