12.8. Blinding and code-breaking

Due to the nature of the DD+ intervention and the usual care control group, patients cannot be blinded to the intervention. Researchers responsible for recruitment, screening, baseline assessment, and scheduling intervention appointments will be unblinded. Researchers conducting outcome evaluations will be blinded to participant allocation, and participants will be instructed not to disclose details of their allocation to the research team at any time during the study.

Blinded statisticians will perform statistical analysis. Qualitative interviews and analysis will be conducted by unblinded researchers.

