12.9. Description of study intervention

DD+ consists of a patient-centred assessment whereby the clinician invites the patient to rate their satisfaction with different life domains and treatment aspects. This is followed by a four-step solution-focused approach to identify the patient's resources and develop solutions to deal with the patient's concerns. The intervention is available as an app and makes use of a tablet computer (e.g. ipad or android device) within routine clinical meetings.

Each session begins with the patient using the tablet to rate their satisfaction with eight life domains (mental health, physical health, job situation, accommodation, leisure activities, friendships, relationship with family/partner, personal safety) and three treatment aspects (medication, practical help, meetings with professionals). The tablet allows patients to be more actively involved in the meeting, with the tablet easily passed between the clinician and patient. Each satisfaction item is rated on a scale from 1 ("totally dissatisfied") to 7 ("totally satisfied"), and followed by a question on whether the patient wants additional help with that domain. The ratings are summarised on screen, allowing for comparisons with ratings from previous meetings. Clinicians are instructed to offer positive feedback on any improving or high-scoring domains.

The ratings are followed by a four-step solution-focused approach to identify the patient's existing resources that can be used to address the concerns raised. The four steps are: Understanding (Why is the patient dissatisfied? What went nevertheless well?); Looking Forward (What is the best-case scenario? What is the smallest step forward?); Exploring Options (What can the patient, the clinician or others do?); and finally Agreeing on Actions (e.g. homework and referrals).

DD+ will be delivered by a blinded trial member once a month for six months in a specific appointment for this purpose.

The control group will continue their routine care in the health centre as indicated by the HC clinical team.

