At visit 6, a researcher will update the CSRI with participants, either at the health centre during the DD+ intervention visit or by phone within five days after the visit.

Visits 3 to 8 – Control group follow-up

Participants allocated to the control group will be followed up on monthly by phone call to assess any health events, and to remind the 6-month follow-up visit.

Visit 9- Main and secondary 6-month outcome assessment.

Within 30 days after Visit 8, a researcher will schedule Visit 9 with participants. The researcher will complete the clinical scales described in Table 1 through patient interviews. Also, HbA1c, HBP and abdominal circumference will be reassessed. For the qualitative implementation assessment, twenty-four patients will be sampled and interviewed as defined in Section 13. Semi-structured interviews will be audio-recorded and are expected to last between 30 and 60 minutes.

Visit 10 and 11- Maintenance period intervention visits

At 90 (± 10) days from visit 9 (visit 10) and 90 (± 10) days from visit 10 (visit 11), participants in the intervention arm will go through the DD+ intervention.

Visits 10 and 11 – Control group follow-up

At 90 (± 10) days from visit 9(visit 10) and 90 (± 10) days from visit 10 (visit 11), participants in the control arm will receive a follow-up phone call.

Visit 12- Main and secondary 12-month outcome assessment

At ± 10 days after visit 11, a researcher will schedule visit 12 with participants. The researcher will complete clinical scales and CSRI through patient interviews. Visit 12 will be the last study visit.

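### The acceptability and appropriateness scales (AIM, IAM) go to DD+ patients only, inside the 6-month outcome visit, and nothing keeps them away from the blinded assessor, so blinding at the primary endpoint is not secured

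*Protocol*

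**What the plan says.** Three places in the Protocol restrict the patient AIM and IAM to one arm:

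- Section 10.1, step a: "At the 6-month assessment, all patients in the intervention arm will complete the AIM and IAM scales".
- Section 13.3.1: "The AIM and IAM instruments will be administered to all participants in the intervention arm".
- Section 13.4, which also fixes the occasion: "all patients in the intervention arm will complete the acceptability and appropriateness scales as part of the outcome assessment visit".

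Table 2 puts AIM and IAM in the 6-month assessment column with MANSA, WHOQOL-BREF, EQ5D, PHQ-8 and GAD-7. The Dialog+ and telephone follow-up rows of that table carry arm-only footnotes. The AIM and IAM rows carry none.

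On the conduct of Visit 9, section 12.10 says: "The researcher will complete the clinical scales described in Table 1 through patient interviews". Table 1 lists AIM and IAM among its outcome measures, under the implementation objective.

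On blinding, section 12.8 says: "Researchers conducting outcome evaluations will be blinded to participant allocation". It adds that "participants will be instructed not to disclose details of their allocation to the research team at any time during the study". The only data collection at 6 months that it releases from blinding is this: "Qualitative interviews and analysis will be conducted by unblinded researchers".

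Section 16 accepts that unblinded patients may overstate quality of life, and offers the blinding of assessors and statisticians as the protection.

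Section 12.9 says of the intervention: "DD+ will be delivered by a blinded trial member once a month for six months in a specific appointment for this purpose".

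**The concern.** According to Table 7, AIM asks about approval and liking of the intervention, and IAM about how well it fits. A patient who is asked these questions is in the DD+ arm, and one who is not asked is a control. A person who administers, opens or collects these forms therefore learns the allocation of every patient seen at Visit 9.

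This matters because the primary outcome is a subjective rating taken at that same visit and patients cannot be blinded. Of the two protections named in section 16, blinded statisticians cannot undo an influence that entered during the interview. Assessor blinding is what protects the measurement itself. PHQ-8, GAD-7, WHOQOL-BREF and EQ-5D-5L are collected at the same visit and share the exposure.

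The wording in section 12.9 adds confusion. Whoever delivers DD+ knows that the patient is in the DD+ arm, so the description as blinded cannot be right.

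**Working it through.** No figure is in dispute, and the sample size does not bear on the point. The check is to set the provisions side by side.

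1. **Who receives the scales?** DD+ patients only (sections 10.1, 13.3.1 and 13.4 agree).
2. **When?** During the 6-month outcome visit (section 13.4; Table 2, 6-month column). MANSA is in the same column.
3. **Do the scales identify the arm?** Yes. Their content concerns the intervention (Table 7) and controls do not get them, so both presence and absence are informative.
4. **Who gives them?** Not stated. Section 13.3.1 says they are administered and section 13.4 says patients complete them; neither names a person. Section 12.10 describes one researcher who completes the clinical scales of Table 1 by interview. Table 1 contains AIM and IAM, but whether the word clinical covers them is open.
5. **In what order?** Not stated. Table 2 lists MANSA near the top and AIM and IAM near the bottom, but it does not present this as an order of administration.
6. **Is there an exception to blinding that covers them?** No. Section 12.8 exempts the qualitative interviews and nothing else at 6 months. It also tells patients not to disclose allocation to the research team, which a patient answering AIM to an assessor would do.
7. **Is there a technical barrier?** None is described. No section says that the forms are hidden from the assessor's REDCap view.

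Steps 1 to 3 establish that the forms reveal allocation. Steps 4 to 7 establish that the Protocol has no provision keeping them from the person it requires to be blinded.

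For the 12-month assessment the chain needs one more link: the same assessor must see the same patient again. The Protocol does not say whether this happens. Table 7 records an interviewer code separately at baseline, 6 and 12 months, so interviewers may differ.

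**The case against.** The strongest reply is that this is an unassigned task and not a breach of blinding. Section 12.10 speaks of clinical scales, and Table 1 puts AIM and IAM under the implementation objective beside the qualitative interviews, apart from MANSA, SIX, PHQ-8 and GAD-7. On that reading the Visit 9 assessor never touches them. Unblinded researchers are already foreseen around this visit for the qualitative interviews. The patient case report form (Annex B) or the operating procedures may settle the matter, and neither is at hand. Even if one person gives everything, the 6-month MANSA is affected only if that person learns the arm before or during it. MANSA is moreover the patient's own rating, completed at screening with the researcher's help, so the assessor's added influence is unknown.

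Most of this stands, and it limits what can be claimed. A reader might infer that the assessor must know the allocation and that blinding is therefore removed at the primary endpoint. The text does not go that far, because it names no administrator and no order. A reader might also infer that the 12-month data are compromised, but no section says the same assessors return. Nor does the error in section 12.9 show that a deliverer would assess outcomes. Elsewhere deliverers are contracted staff trained in DD+, and no section gives them that role.

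The objection does not supply the missing safeguard. The exception in section 12.8 leaves out AIM and IAM, and sites would have to invent the separation themselves. Giving the scales last would help only if the assessor did not know beforehand which patients were due to receive them.

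**Conclusion.** The point holds as a gap in the blinding procedure. As written, the assessor blinding that section 16 relies on is not secured at the 6-month primary endpoint. If the Visit 9 assessor handles AIM and IAM, the arm is revealed for every attendee. The 12-month assessment is exposed only if that assessor returns. In addition, section 12.9 contains a plain error in calling the DD+ deliverer blinded.

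The size of any bias in MANSA cannot be estimated from the document. It is tempting to assume an interviewer effect and compare it with the 0.4-point target difference, but the Protocol gives no basis for such a value and the conclusion does not need one.

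The conclusion assumes that the annexed forms and operating procedures, which were not available, do not already separate these scales from the assessor. If they do, the Protocol still needs to say so. The design, sample size and analysis are unaffected. The correction should be made before the first Visit 9, because unblinding at that visit cannot be repaired afterwards.

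**What to change.** - **Section 13.4 and section 12.10, Visit 9:** state that AIM and IAM are completed privately by the patient, or given by the unblinded researchers already in place, and only after all Visit 9 outcomes are completed and locked.
- **REDCap:** hide the AIM and IAM forms, and their completion status, from the blinded assessor's role.
- **Section 12.8:** extend the exception for qualitative interviews to AIM and IAM.
- **Table 2:** mark the AIM and IAM rows as intervention arm only, as is done for the Dialog+ row.
- **Section 12.9:** say that the person delivering DD+ is unblinded and takes no part in outcome assessment.

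The cost is a small change in visit logistics, a REDCap role setting and a few lines of text. It uses unblinded staff the trial already has and loses no data.

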14. SAFETY REPORTING

The study will take place within the context of the primary care and mental health care systems in Colombia, where a resource-oriented intervention will be evaluated for its effectiveness. The interventions and research assessments will take place in addition to routine health treatment. Adverse Events, immediate hazards or the need for Urgent Safety Measures are not anticipated.

14.1. Serious Adverse Events

14.1.1. Definition of Serious Adverse Events

A serious adverse event is any untoward medical occurrence that:

- results in death
- is life-threatening
- requires inpatient hospitalisation or prolongation of existing hospitalisation
- results in persistent or significant disability/incapacity
- consists of a congenital anomaly or birth defect.

Other 'important medical events' may also be considered a serious adverse event when, based upon appropriate medical judgement, the event may jeopardise the participant and may require medical or surgical intervention to prevent one of the outcomes listed above.

14.1.2. Reporting Procedures for Serious Adverse Events

A SAE occurring to a participant should be reported to the REC/IRB that gave a favourable opinion of the study. Reports of related and unexpected SAEs should be submitted within seven working days of the PI becoming aware of the event. Local investigators should inform the PI immediately after becoming aware of the event and within the first 24 hours of identifying the SAE.

Based on previous safety reports and research experience with DD+, a low likelihood of a 'related' event is expected.

14.1.3. Follow-up of Serious Adverse Events.

After the initial SAE report, investigators will proactively follow up with each participant by fortnightly phone calls until the issue is resolved. The local research team will ensure participants receive appropriate medical treatment and follow-up as required, according to each participant's medical insurance, until resolution.

14.2. Adverse Events

14.2.1. Adverse Event Definition

In the context of a psychosocial intervention such as DD+, an AE will be defined as an untoward event, unfavourable change, unwanted medical occurrence, or unintended sign or symptom having been absent at baseline, or, if present at baseline, appears to worsen and is temporally associated with the intervention (48). The adverse event does not necessarily have a causal relationship with the intervention.

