| GAD-7 | | X | | | | | | | | X | | | X |
| AUDIT-C | | X | | | | | | | | X | | | X |
| HbA1 measurement | | X | | | | | | | | X | | | X |
| HBP measurement | | X | | | | | | | | X | | | X |
| Obesity assessment | | X | | | | | | | | X | | | X |
| Eligibility checklist | | X | | | | | | | | | | | |
| SIX | | | X | | | | | | | X | | | X |
| CSRI | | | | X | | | | | | X | | | X |
| AIM | | | | | | | | | | X | | | |
| IAM | | | | | | | | | | X | | | |
| Dialog+** | | | | X | X | X | X | X | X | | X | X | |
| Telephone follow-up¥ | | | | X | X | X | X | X | X | | X | X | |
| Qualitative Interview¶ | | | | | | | | | | X | | | |

Abbreviations: M=Month; D=Day; Int= Intervention DIALOG+; M.Int = Maintenance Intervention DIALOG+; PHQ-8=Patient Health Questionnaire-9; GAD-7=Generalized Anxiety Disorder-7; HBP= High Blood Pressure; SIX=Objective Social Outcomes Index; CSRI= Client Service Receipt Inventory; AIM= Acceptability of Intervention Measure; IAM= Intervention Appropriateness Measure; FIM= Feasibility Intervention Measure; 6-MA: six months assessment.

*The screening visit and baseline visit may be performed on the same day or on a different day.

**Intervention arm only

¥Control arm only

¶A sample of 24 patients allocated to the intervention group will be interviewed. The window for qualitative interviews can be extended by 15 additional days beyond the indicated timeframe.

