- The researcher will screen participants for diabetes, obesity and HBP following standard procedures. The diagnosis will be assessed based on the in-situ screening or a previously reported and confirmed diagnosis by the healthcare provider. Screening criteria are presented in **Table 3**.
 - a. The researcher will take a capillary blood sample for assessing HbA1c levels ([Afinion™ HbA1c Abbott](#)),
 - b. Measure blood pressure with standard electronic equipment. During the visit, the assessment will be done at three moments, with at least five minutes between measurements. HBP measurement will follow the checklist and recommendations from the 2025 AHA Guideline for the Prevention, Detection, Evaluation, and Management of HBP, as well as the established study standard procedures (46).

- c. Record abdominal circumference measuring at the midway between the bottom of the ribs and the top of the hips, while the participant breathes out naturally, before taking the measurement (47).
- d. Record height and weight using validated instruments and as stated in the standard procedures.

The screening visit is finalised with the determination of the participant's eligibility. The assessment will be made by the researcher after filling out the selection criteria checklist.

Visit 2- Baseline Assessment Visit

Depending on logistical issues and the availability of the research team and participants, the screening visit and baseline assessment may be performed on the same day or a different day, considering a window of no more than ten calendar days. The baseline consists of the completion of a sociodemographic questionnaire and the remaining instruments for this visit (EQ5D, WHOQOLBREF, SIX, CSRI). The researcher will complete the baseline assessment through a patient interview. This process will take approximately 60 minutes. Visit 2 finalise with participant randomisation.

Visits 3 to 8 – Intervention visits

After randomisation, visits 3 to 8 will take place once a month (average month duration of 30 calendar days), with a 10-day window.

- Patients will be assigned to a routine clinical visit with a trial clinician. The local trial research coordinator will facilitate the appointment assignment.
- A member of the research team will accompany the patient and clinician to support them in any technical or logistical issues.
- Patient and clinician will privately go through the intervention meeting: DD+ with the solution-focused approach.

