14.2.2. Reporting Procedures for Adverse Events

AEs occurring to a participant will be recorded in the main research file (REDCap) and the participant's clinical records, if appropriate. Reports of AE should be submitted as soon as possible to the local PI and CIs after being identified by a researcher and within the next seven working days.

Based on previous safety reports and research experience with DD+, a low likelihood of a 'related' event is expected. Due to the nature of the intervention and the low risk of AE, causality assessment will be jointly conducted by the local PI and CI within the next 30 working days after the report.

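### The adverse event definition and the scheduled health-event enquiry both differ by arm, so non-serious adverse event rates will not be comparable

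*Protocol*

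**What the plan says.** **Definition.** Protocol section 14.2.1 covers two kinds of AE: something absent at baseline, and something present at baseline that "appears to worsen and is temporally associated with the intervention". It adds: "The adverse event does not necessarily have a causal relationship with the intervention".

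**Control contacts.** Under section 12.10, controls at visits 3 to 8 "will be followed up on monthly by phone call to assess any health events", and are reminded of the 6-month visit. At visits 10 and 11, "participants in the control arm will receive a follow-up phone call", with no content stated. The telephone follow-up row of Table 2 (section 10.1) carries the footnote "Control arm only".

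**DD+ contacts.** For visits 3 to 8, section 12.10 lists appointment assignment, attendance by the research team, the DD+ session, and an update of the service-use inventory (CSRI) at visit 6. On attendance it says: "A member of the research team will accompany the patient and clinician to support them in any technical or logistical issues". No health-event question is listed for these visits or for the DD+ sessions at visits 10 and 11.

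**Recording.** Section 14.2.2 records AEs for any participant, without regard to arm, once a researcher has identified the event. Neither Table 2 nor Table 7 has an AE row.

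**The concern.** An AE rate in the DD+ arm can be interpreted only against the background rate in controls. That requires the same event to count, and to have the same chance of being found, in each arm. Here both conditions depend on allocation.

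The point has some weight in this trial. Sections 2.1.1 and 21.5 of the protocol recognise that DD+ may provoke anxiety or distress. Section 18.3 dispenses with a data monitoring committee and relies on the safety reporting section. Section 14.2.2 has the local principal investigator and the chief investigator judge causality, and they would do so without a sound background rate of non-serious events. An event that was never asked about, or that the definition excluded, cannot be recovered at analysis, so a statistical analysis plan cannot repair this.

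**Working it through.** The protocol gives no expected AE rate, so there is no figure of its own to reproduce. The check sets the text side by side and then shows how far unequal capture alone could move a comparison.

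**Step 1: which events count.** The temporal clause can be read as qualifying only worsening (reading A) or every AE (reading B).

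| Event | DD+ arm | Control, reading A | Control, reading B |
|---|---|---|---|
| New since baseline | can count | counts | no intervention to refer to |
| Worsening of a baseline condition | can count | no intervention to refer to | no intervention to refer to |

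Worsening in a control has no clear status on either reading. The sentence that no causal link is needed does not help, because the temporal link still refers to the intervention. Worsening is also a large category here. Section 11.3.1 requires each participant to have a physical condition and a mental health condition, diagnosed or found on screening, and a MANSA score of 5 or less.

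**Step 2: which events are asked about.**

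| Contact | Control | DD+ |
|---|---|---|
| Visits 3 to 8 (six) | call that asks about health events | session; no event question listed |
| Visits 10 and 11 | call, content not stated | session; no event question listed |
| Visits 9 and 12 | common assessment | common assessment |

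Between baseline and 6 months there are thus six scheduled event enquiries in controls and none in the DD+ arm. No AE row in Table 2 evens this out at months 6 and 12.

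**Step 3: direction.** The schedule favours detection in controls. The definition favours the DD+ arm, and monthly face-to-face contact may do so too. The net sign cannot be known in advance.

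**Step 4: possible size (illustration only).** Let p be the same true risk in both arms, and let s be the proportion of events that are both found and counted. The missing question lowers s in the DD+ arm; the definition lowers s in controls. Then

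apparent risk ratio = (p × s_DD+) / (p × s_control) = s_DD+ / s_control.

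The true risk cancels. The values of p and s are assumptions. The 113 per arm comes from section 15.2 (90 / 0.80 = 112.5, rounded up).

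- s_control = 0.90, s_DD+ = 0.70: ratio 0.70 / 0.90 = 0.78.
- s_control = 0.90, s_DD+ = 0.50: ratio 0.50 / 0.90 = 0.56.
- Imbalance reversed: 0.90 / 0.70 = 1.29 and 0.90 / 0.50 = 1.80.

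At p = 0.20, the expected count in controls is 113 × 0.20 × 0.90 = 20.3. In the DD+ arm it is 113 × 0.20 × 0.70 = 15.8 or 113 × 0.20 × 0.50 = 11.3. With p = 0.10 the counts are 10.2 against 7.9 or 5.7; with p = 0.30 they are 30.5 against 23.7 or 16.9. In every case the true difference is zero.

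**Step 5: what is unaffected.** The serious adverse event (SAE) definition in section 14.1.1 does not mention the intervention. Table 7 collects PHQ-8, GAD-7, AUDIT-C, HbA1c, blood pressure and CSRI service use at baseline, 6 and 12 months, and death status at 12 months, for all participants.

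**The case against.** The strongest reply is that harms remain visible. A reader might infer from the unequal AE rules that harms cannot be compared between arms at all, or that recorded AEs are the only safety evidence. The protocol does not support either inference. SAEs are defined without reference to arm, and the measures in Table 7 give worsening depression, anxiety or glycaemia a randomised comparator at 6 and 12 months. Section 12.8 plans blinded outcome assessors. This part of the reply stands and limits the point to non-serious AEs. One gap remains: SAEs between assessments still come to light through the same unequal enquiry.

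A reader might also infer that no event in a control can be an AE. On reading A, which is a natural one, new events in controls do count. The difficulty is certain only for worsening.

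Nor should one assume that nothing is captured in the DD+ arm. Section 12.9 has participants rate mental health, physical health and medication at every session, and a researcher attends. Events may well be volunteered. But these are satisfaction ratings, the researcher's listed role is technical or logistical, and nothing requires the question to be asked.

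Finally, the patient case report form (Annex B) is not shown and may contain an event item, and no objective in Table 1 compares AE rates. The first is possible, but the protocol's visit procedures should then say so. The second lowers the stakes without removing the need for a usable background rate.

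**Conclusion.** The point holds for non-serious AEs. As written, what counts as an AE and who is asked about it both depend on the arm, so a comparison of non-serious AE rates would be biased in an unknown direction. Detection of SAEs between assessments rests on the same unequal enquiry.

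The size cannot be derived from the protocol. The apparent ratios of 0.56 to 0.78, or 1.29 to 1.80 in reverse, rest wholly on assumed capture of 90% against 50% to 70%. They show what is possible and are not estimates. The conclusion on enquiry assumes that the visits are run as section 12.10 lists them.

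SAEs as defined, deaths, CSRI service use, symptom scores and clinical measures can be compared at the common assessments. The defect is modest and the remedy cheap, but it has to be applied before recruitment.

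**What to change.** 1. In section 14.2.1, define an AE as any untoward occurrence, or worsening of an existing condition, after randomisation in either arm. Remove the temporal link to the intervention and judge relatedness as a separate step, which section 14.2.2 already provides for.
2. In section 12.10 and Table 2, add one short health-event question with identical wording in both arms: at DD+ visits 3 to 8, 10 and 11, and at the matching control calls. State the content of the control calls at visits 10 and 11.

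The cost is one definition edit, one form item at contacts that already take place, and a few more non-serious AEs to log. Treatment, sample size and visit schedule do not change.
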